3. INVESTIGATIONAL PLAN

3.1 Study Design and Duration

This is a Phase 2, multi-center, open-label, multiple cohort study of elotuzumab in combination with pomalidomide and low-dose dexamethasone (EPd Cohort) and elotuzumab in combination with nivolumab (EN Cohort) to assess the safety and efficacy of these combination therapies for treatment of relapsed or refractory MM patients.

In the EPd Cohort, subjects will receive treatment with elotuzumab in combination with pomalidomide and low-dose dexamethasone in a 28 day cycle. Subjects will receive 10 mg/kg IV elotuzumab on Days 1, 8, 15, and 22 of Cycles 1 and 2. Starting with Cycle 3, subjects will receive 20 mg/kg on Day 1.

As of Amendment 02, subjects will also be enrolled in the EN cohort to receive a combination of elotuzumab and nivolumab in a 28-day cycle. EN subjects will receive nivolumab 240 mg IV on Days 1 and 15 for Cycles 1-4. At Cycle 5 and beyond, subjects will receive 480 mg IV on Day 1. Subjects will also receive elotuzumab 10 mg/kg on Days 1, 8, 15, and 22 of Cycles 1 and 2. At Cycle 3 and beyond, subjects will receive 20 mg/kg of elotuzumab IV on Day 1. If subjects do not achieve clinical benefit represented by at least minimal response (\geq MR) after 2 cycles of treatment or do not achieve an objective response (\geq PR) after 5 cycles of treatment, they may cross over to the EPd cohort at Day 1 of the subsequent cycles if they also meet the eligibility criteria for cross-over specified in Section 3.3.4.

Subjects will continue treatment as long as the subject has clinical benefit from the treatment and do not meet criteria for discontinuation.

All subjects will be assessed for safety and response as presented in the Time and Event Tables in Section 5. Subjects who are discontinued from further study treatment for reasons other than progression will be followed for disease progression. Following disease progression, subjects will be followed at least annually for survival.

Approximately 120 subjects will be screened in this study. A minimum of 60 subjects will be treated in the EPd Cohort. Approximately 30 subjects will be treated in the EN Cohort. The estimated duration of enrollment is 18 to 24 months, and the duration of the study is estimated at 48 months from the date of first patient, first visit. Per Revised Protocol 03, the EPd cohort is closed for enrollment.

The study design schematic is presented in Figure 3.1-1.

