3.3.3 Women of Childbearing Potential

A Women of childbearing potential (WOCBP) is defined as any female who has experienced menarche and who has not undergone surgical sterilization (hysterectomy or bilateral oophorectomy) and is not postmenopausal. Menopause is defined as 12 months of amenorrhea in a woman over age 45 years in the absence of other biological or physiological causes. In addition, females under the age of 55 years must have a serum follicle stimulating hormone, (FSH) level > 40mIU/mL to confirm menopause.

*Females treated with hormone replacement therapy, (HRT) are likely to have artificially suppressed FSH levels and may require a washout period in order to obtain a physiologic FSH level. The duration of the washout period is a function of the type of HRT used. The duration of the washout period below are suggested guidelines and the investigators should use their judgment in checking serum FSH levels. If the serum FSH level is > 40 mIU/ml at any time during the washout period, the woman can be considered postmenopausal:

• 1 week minimum for vaginal hormonal products (rings, creams, gels)

- 4 week minimum for transdermal products
- 8 week minimum for oral products

Other parenteral products may require washout periods as long as 6 months.

3.3.4 Eligibility Criteria for EN Patients to Cross-over to EPd cohort.

Crossover to EPd is permitted if:

- No clinical benefit (\geq minimal response) after 2 cycles.
- No objective response (\geq PR) after 5 cycles of treatment.

EN patients who cross-over will no longer be treated with nivolumab after the cross-over to the EPd cohort. Re-consent is not required for EN patients who cross-over to treatment with EPd.

EN patients who do not cross-over can continue treatment with EN until discontinuation criteria are met, as specified in Section 3.5.

Eligibility criteria for this study have been carefully considered to ensure the safety of the study subjects and that the results of the study can be used. It is imperative that subjects fully meet all eligibility criteria.

	_	

Revised Protocol No.: 03 Date: 08-Mar-2018

Revised Protocol No.: 03 Date: 08-Mar-2018

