2 STUDY DESCRIPTION

2.1 Study Design

This is a Phase 2, multi-center, open-label, multiple cohort study of elotuzumab in combination with pomalidomide and low dose dexamethasone (EPd Cohort) and elotuzumab in combination with nivolumab (EN Cohort) to assess the safety and efficacy of this combination therapy for treatment of relapsed or refractory MM patients.

Approximately 100 subjects will be screened in this study. A minimum of 60 subjects will be treated in the EPd Cohort. Approximately 25 subjects will be treated in the EN Cohort. The estimated duration of enrollment is 18 to 24 months, and the duration of the study is estimated at 48 months from the date of first patient first visit.

The study design schematic is presented in Figure 3.

Figure 3:Study design Schematic

In the EPd Cohort, subjects will receive treatment with elotuzumab in combination with pomalidomide and low-dose dexamethasone in a 28 day cycle. Subjects will receive 10 mg IV

elotuzumab on Days 1, 8, 15, and 22 of Cycles 1 and 2. Starting with Cycle 3, subjects will receive 20 mg/kg on Day 1. As of Amendment 02, subjects who progress as defined by IMG criteria in the EPd cohort will be eligible to add nivolumab 240 mg every 2 weeks (Q2W) on Days 1 and 15 of each cycle.

As of Amendment 02, subjects will also be enrolled in the EN cohort to receive a combination of elotuzumab and nivolumab in a 28-day cycle. Subjects will receive nivolumab 240 mg IV on Days 1 and 15 for Cycles 1-4. Starting with Cycle 5 and beyond, subjects will receive 480 mg IV on Day 1. Subjects will also receive elotuzumab 10 mg on Days 1, 8, 15, and 22 of Cycles 1 and 2. Starting with Cycle 3 and beyond, subjects will receive 20 mg of elotuzumab IV on Day 1. If subjects do not achieve clinical benefit represented by at least minimal response (\geq MR) after 2 cycles of treatment, or do not achieve an objective response (\geq PR) after 5 cycles of treatment, they may cross over to the EPd cohort at Day 1 of the subsequent cycles if they also meet the eligibility criteria for cross-over specified in protocol Section **Error! Reference source not found.**

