7 STATISTICAL ANALYSES

7.1 General Methods

Continuous variables will be summarized using descriptive statistics; i.e. number of non-missing observations (n), mean, standard deviation (STD), median, minimum, maximum, first quartile

and third quartile. The number of decimal places displayed in all listings will be determined by the number of decimal places in the raw data. Unless otherwise specified, minimum and maximum will be reported to the precision as the data collected, one more decimal place for the mean and median, and two more decimal places for the standard deviation. The adjusted geometric mean, geometric mean ratio and the lower and upper limits of confidence interval will be displayed to three decimal places. Categorical variables will be summarized by frequencies and percentages.

Safety analyses will be conducted on all treated subjects. Efficacy analyses will be conducted on all treated subjects, and also by subgroups based on lines of prior therapy (2L, 3L), or by age group (<65 years, \geq 65 years), and (<75 years, \geq 75 years). Descriptive statistics (n, mean, median, standard deviation, minimum, maximum or interquartile range) will be provided. Because the sample size for the study is small, summary statistics with their associated 95% confidence intervals and tests of hypotheses will be based, to the extent possible, using small-sample statistics like the Clopper- Pearson for binomial data. Median time-to-event and its 95% confidence interval will be based on the Kaplan-Meier (KM) estimation procedure. The KM curves will be presented for time to event endpoints. Separate analyses will be conducted for each cohort EPd and EN.

Laboratory results, adverse events, and other symptoms will be graded using the National Cancer Institute (NCI) Common Terminology Criteria for Adverse Events (CTCAE), version 3.0, except where CTCAE grades are not available. Individual laboratory values will be presented in both the International System of Units (SI) and US unit (US). Adverse events will be categorized using the most current version of Medical Dictionary for Regulatory Activities (MedDRA), by system organ class and preferred term. Prior therapies will be summarized using the most current version of the World Health Organization (WHO) drug dictionary.

Statistical analyses will be carried out in SAS (Statistical Analysis System, SAS Institute, North Carolina, USA), unless otherwise indicated.

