7.6 Safety

7.6.1 Adverse Events

AEs will be categorized using the most recent version of the MedDRA, by system organ class (SOC) and preferred term. The severity of AEs will be graded using the NCI CTCAE (v 3.0).

On-study AEs are defined as non-serious and serious AEs with an onset date on or after the first dose until 60 days after the last dose. See Section 8.4, Imputing AE Onset Dates, for a discussion of imputation rules for incomplete or missing AE onset dates. If the relationship to study drug is missing, then the AE will be assumed to be related to study drug.

Unless specified otherwise, AEs will be counted only once within each SOC and preferred term, according to their worst CTC grade.

Tables will be sorted by SOC and preferred term, with SOCs ordered by decreasing frequency overall and then alphabetically. Preferred terms will be sorted within SOCs by descending frequency overall and then alphabetically.

Frequency table of the worst grade of on-study AE will be presented. The table will be with AEs broken out by individual grade, 1, 2, 3, 4 or 5 together with an Any Grade category. There will also be a table in which grades are grouped as follows "Any, Grade 3-4 and Grade 5". This last summary will be repeated for on-study drug-related AEs.

A by-subject listing all AEs will be presented for all treated subjects.

In addition the following will be presented:

• Exposure-adjusted AE incidence rates (including multiple occurrences of unique events) will be calculated for each SOC and preferred term.

Exposure-adjusted incidence rate per 100 person-years will be used and will be calculated as:

 $100 \times \frac{\text{Total number of unique AEs}}{\left(\frac{\text{subject date of last dose of study drug} - \\ \frac{\text{subject date of first dose of study drug} + 60 + 1}{365.25}\right)}$

and will be displayed along with a count of events

AEs can be counted multiple times within each SOC and preferred term in this summary table.

A by-subject listing of unique AEs will be provided for all treated subjects.

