7.6.4 Deaths

The number and percentage of deaths and the investigator-reported cause of death will be presented. This will be summarized for all deaths, and for those reported on study treatment or within 60 days of discontinuing study treatment.

A by-subject listing will be provided and will present date of death and reason of death.

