7.6.5 Clinical Laboratory Evaluations

On-treatment laboratory tests for safety are defined as those that occur after first dose of any study therapy until 60 days after last dose of any study therapy.

The number and percentage of subjects with each worst severity grade for on-study hematology parameters (hemoglobin, WBC, ANC, ALC and platelets) will be presented. Grades will be categorized as Grade 1, Grade 2, Grade 3, Grade 4, Any Grade and Grade 3-4. Subjects will be counted only once for each parameter, according to their worst post baseline CTC grade. The percentage of subjects with each worst severity grade will be calculated out of the number of all treated subjects with on-study assessment for lab parameter. Subjects without post-baseline (on-treatment) assessment for a lab parameter will be reported in the "NOT REPORTED" category.

This summary will be repeated for:

- Liver parameters (ALT, AST, alkaline phosphatase, albumin and total bilirubin) with available CTC grades
- Renal/electrolyte parameters (sodium, potassium, bicarbonate, calcium, glucose and creatinine) with available CTC grades

Sodium, potassium, calcium, and random glucose will be presented separately, based on their high and low values.

For blood urea nitrogen (BUN), direct bilirubin and total protein the worst category on-treatment will be presented. Results will be categorized as; below upper normal limits, above upper normal limits or not reported.

For reporting purposes, urea will be converted to BUN, using the conversion factor: urea (mmol/L) / 0.357 = BUN (mg/dL)."

Subjects experiencing any potential drug induced liver injury (DILI) will be summarized by treatment group and overall as follows:

• A summary of the number and percentage of subjects with (AST or ALT > 3 x upper limit of normal (ULN)) and (Total bilirubin > 2 x ULN and ALP < 2 x ULN) will be presented.

If any potential cases of DILI are identified then clinical review will be conducted to ensure no other immediate apparent possible causes of AT elevation and hyperbilirubinemia are present, including but not limited to, viral hepatitis, pre-existing chronic or acute liver disease, or the administration of other drugs known to be hepatotoxic.

Note: The timing for total bilirubin rising to $> 2 \times ULN$ needs to be concomitant with or within 30 days after ALT or AST rising to $> 3 \times ULN$. ALP needs to be $< 2 \times ULN$ at the time of or

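### The SAP's safety windows have no cut at the EN-to-EPd crossover, so the planned by-cohort tables do not separate the toxicity of the two regimens

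*SAP*

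**What the plan says.** Protocol 3.1 states the study's aim as "to assess the safety and efficacy of these combination therapies for treatment of relapsed or refractory MM patients", so each regimen has its own safety question.

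SAP 2.1 describes EN subjects without sufficient response after 2 or 5 cycles and says "they may cross over to the EPd cohort at Day 1 of the subsequent cycles". Protocol 3.3.4 adds: "EN patients who cross-over will no longer be treated with nivolumab after the cross-over to the EPd cohort". Protocol Table 4.5-1 then puts these subjects on the EPd schedule for Cycle 3 and beyond, with pomalidomide and weekly dexamethasone.

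The SAP's safety rules are:

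- 7.6.1: on-study AEs are those "with an onset date on or after the first dose until 60 days after the last dose", counted once per system organ class and preferred term at worst grade. The exposure-adjusted rate divides by last dose minus first dose of study drug, plus 60 + 1 days.
- 7.6.2: SAEs and AEs leading to discontinuation use the same on-study term.
- 7.6.4: deaths are counted overall, and separately if on treatment or "within 60 days of discontinuing study treatment".
- 7.6.5: on-treatment laboratory tests are "those that occur after first dose of any study therapy until 60 days after last dose of any study therapy", summarized at worst grade.

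On reporting, SAP 7.1 says "Separate analyses will be conducted for each cohort EPd and EN". It does not say to which cohort a crossed-over subject's later events belong.

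**The concern.** At crossover nivolumab stops, pomalidomide starts, and dexamethasone changes from an intravenous premedication to a weekly part of the treatment. A window that starts at the first EN dose and ends 60 days after the last EPd dose contains both regimens. Worst-grade counting then reduces them to one entry per term.

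EN is the experimental combination. Protocol 1.5 expects no increase in toxicity from joining the two antibodies, but also warns that unforeseen events may occur. To judge that expectation, even descriptively, a reader needs EN tables that contain EN experience. The opposite mixing also matters. Under Protocol 3.3.1, EN subjects have at least 4 prior lines and EPd subjects 1 or 2, so adding crossed-over subjects to the EPd tables changes the population those tables describe.

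SAP 7.6.3 does not fill the gap. Its events of special interest are infusion reactions and second primary malignancies, with no display of immune-related events or of events timed from the last nivolumab dose.

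**Working it through.** The plan states no figure on this point, so there is nothing to reproduce. The check has three steps.

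**1. Does the window span both regimens?** Protocol Section 4 lists elotuzumab, nivolumab, dexamethasone and pomalidomide together as study drug. A crossed-over subject's first dose is an EN dose and the last is an EPd dose. Elotuzumab continues across the switch, so a window tied to elotuzumab alone would span it too. Only the laboratory rule refers explicitly to any study therapy. The AE rule speaks of the last dose, and the rate formula of the last dose of study drug. None of them mentions crossover.

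**2. How much of the window lies after crossover?** Inputs: 28-day cycles; crossover after c = 2 or 5 EN cycles (SAP 2.1); the SAP 7.6.1 window, last dose − first dose + 60 + 1. Assumptions: crossover on Day 1 of the next cycle, k EPd cycles, and last dose on Day 22 of the last one.

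- Study day of last dose = 28c + 28(k − 1) + 22
- Window = that day − 1 + 60 + 1
- EN days = 28c
- Share after crossover = (window − EN days) / window

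Example, c = 2 and k = 1: last dose on day 56 + 0 + 22 = 78; window = 78 − 1 + 61 = 138; share = (138 − 56)/138 = 59%.

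| EN cycles | EPd cycles | Window (days) | EN days | Days after crossover | Share after |
|---|---|---|---|---|---|
| 2 | 1 | 138 | 56 | 82 | 59% |
| 2 | 2 | 166 | 56 | 110 | 66% |
| 2 | 6 | 278 | 56 | 222 | 80% |
| 2 | 12 | 446 | 56 | 390 | 87% |
| 5 | 1 | 222 | 140 | 82 | 37% |
| 5 | 2 | 250 | 140 | 110 | 44% |
| 5 | 6 | 362 | 140 | 222 | 61% |
| 5 | 12 | 530 | 140 | 390 | 74% |

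The days after crossover include the 60-day tail. These are shares of time, not of events.

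**3. How different is treatment after the switch?** Dexamethasone can be compared with the SAP's own factor of 1.32 mg oral per mg intravenous (SAP 7.4.1.10) and Protocol Tables 4.5.2-1 and 4.5.2-2. Planned dose per cycle from Cycle 3:

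- EN: 8 × 1.32 = 10.56 mg
- EPd, age 75 or under: 28 + 8 × 1.32 + 3 × 40 = 158.56 mg
- EPd, over 75: 8 + 8 × 1.32 + 3 × 20 = 78.56 mg

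Pomalidomide is added on Days 1–21, and nivolumab is withdrawn.

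**The case against.** A reader might infer that post-crossover toxicity will be reported as EN toxicity, and that the EN safety question therefore cannot be answered. The documents do not support that. The SAP is silent on attribution, and Protocol Tables 4.5-1 and 5.1-3 group crossed-over subjects with EPd for dosing and visits. By-subject listings of AEs, SAEs, deaths and laboratory data are planned, and dosing dates are recorded, so a split remains possible. Subjects who do not cross over are unaffected. Crossover is optional, and Protocol 3.5 requires discontinuation at progression, so the number crossing may be small. An uncontrolled cohort of about 30 could not formally test the expectation of no added toxicity in any case. Nor is it right to say that full-dose dexamethasone is started, since the documents call the EPd dose low.

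All of that stands, but it does not remove the problem. Grouping for dosing and visits is not a rule for analysis. If these subjects are counted under EPd, the stated window still starts at their first dose and brings EN-period events with it. A split made later from listings would be an unplanned choice made with the data in hand. SAP Section 9 leaves table detail to a Data Presentation Plan, but nothing shows that it supplies this rule.

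The protocol's nivolumab-based windows help only in part. They are the stopping rule in 4.5.10 and the 100-day follow-up for those who stop EPd within 2 cycles. The SAP uses neither, and 100 days is about 3.6 cycles (100/28), so events in that window can arise on EPd.

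**Conclusion.** The point holds as a gap in the analysis rules. Followed as written, SAP 7.6.1, 7.6.2, 7.6.4 and 7.6.5 give mixed-regimen safety figures for every crossed-over subject, whichever cohort that subject is counted in. The exposure-adjusted rate is mixed in both numerator and denominator, so the direction of its error cannot be predicted.

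The effect on reported event rates is unknown. The documents give neither a crossover count nor event rates, and any percentage-point figure would rest on assumption alone. What can be computed is the share of a crossed-over subject's window that falls after the switch: about 37% to 87%, on the assumed timing and 1 to 12 EPd cycles.

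A related conflict is in the text itself. The SAP uses 60 days after last dose throughout (4.6, 6.1, 7.6.1, 7.6.4, 7.6.5), while Protocol 6.2.1 and 8.4.3 set 100 days for EN.

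**What to change.** State the following in SAP 7.6.1 to 7.6.5 for EN subjects who cross over:

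- **Cut date.** Split the window at the first dose of any drug given under the EPd schedule: Day 1 of the crossover cycle, including its oral dexamethasone premedication. The first pomalidomide dose would be too late a cut. Protocol 4.5.1 and 4.5.2 place it after that day's elotuzumab, and the oral dexamethasone 3 to 24 hours before elotuzumab.
- **EN tables.** Include AEs, SAEs, AEs leading to discontinuation, deaths and laboratory values from the EN period only, with worst grade taken within that period. Person-time for these subjects ends at the crossover date, without the added 60 days.
- **Crossover column.** Report later events separately, not pooled with the original EPd cohort. Within this column, also show events with onset within 100 days of the last nivolumab dose. This needs no immune-related category, which SAP 7.6.3 does not define.
- **Window length.** Reconcile the SAP's 60 days with the protocol's 100 days for EN.

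The cost is SAP wording and one extra column from dates already collected. The downside is that crossed-over subjects have shorter EN follow-up than the others, with no post-treatment tail. A table footnote should say so.

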6.2.1 Nonserious Adverse Event Collection and Reporting

The collection of nonserious AE information should begin at initiation of study drug until 60 days from the last dose of study drug for patients in the EPd cohort and until 100 days from the last dose of study drug for the EN cohort. Subjects in the EN cohort who cross-over to the EPd cohort but discontinue treatment within 2 cycles of EPd treatment will still need to undergo 100 day follow-

up visit from last dose of the nivolumab to evaluate safety events related to study treatment. Nonserious AE information should also be collected from the start of a placebo lead-in period or other observational period intended to establish a baseline status for the subjects.

Nonserious AEs should be followed to resolution or stabilization, or reported as SAEs if they become serious (see Section 6.1.1). Follow-up is also required for nonserious AEs that cause interruption or discontinuation of study drug and for those present at the end of study treatment as appropriate. All identified nonserious AEs must be recorded and described on the nonserious AE page of the CRF/eCRF (paper or electronic).

Completion of supplemental CRF/eCRFs may be requested for AEs and/or laboratory abnormalities that are reported/identified during the course of the study.

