8.4.2 Efficacy Analyses

The efficacy endpoints, PFS and ORR, will be defined using the IMWG criteria. Responses will be assessed at every treatment cycle using central laboratory test results on myeloma urine and serum, local laboratory bone marrow aspiration test, and if needed bone marrow and skeletal survey results and CT/MRI assessments. Objective responses will include stringent complete

```
Revised Protocol No.: 03
Date: 08-Mar-2018
```

response, complete response, very good partial response and partial responses. The ORR and its 95% confidence interval (CI) using the Clopper-Pearson estimation procedure will be reported. PFS and OS will be plotted using Kaplan-Meier estimates, and if estimable, median and its 95% CI will be reported. Time to response will be analyzed for responders only with summary statistics provided. Duration of response will be reported using K-M estimates. The time to event responses will be recorded from the first day of the first cycle to the day that an event occurs. If no event occurs by the time the study is completed, the patient is censored for that event at the last day of subject contact.

For EPd cohort, the primary analysis of PFS will be conducted when 48 progression events have been observed.

For EN cohort, the primary analyses for ORR will be conducted when enrollment in the EN cohort is complete and all enrolled patients treated with the combination have received at least 3 cycles of treatment.

MRD negativity status for subjects in the EN Cohort will be evaluated by time points. The frequency of the MRD negativity status and the best MRD negativity status will be summarized for the EN cohort. The cross tabulation of the MRD negativity status and BOR will be presented. Summary statistics of the MRD levels and their corresponding percent changes from baseline will be tabulated by planned study day for the EN cohort. Potential association between the first/best MRD negativity status with PFS and OS will be evaluated in all treated patients. Additional details will be presented in the Statistical Analysis Plan.

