The pomalidomide dose intensity, per subject, will be calculated as:

7x[cumulative dose of pomalidomide / (min(date of first dose of Pomalidomide in the last cycle in which Pomalidomide was administered+28, discontinuation date, death date) - date of first dose of Pomalidomide)]

The relative dose intensity of pomalidomide is the dose intensity per week divided by the planned dose intensity per week, 21mg times 100%.

Dexamethasone:

The dose intensity (mg/week) of dexamethasone, per subject, will be calculated separately for the period encompassing Cycles 1 and 2 and for the periods from Cycles 3 and beyond.

Cycle 1 and 2:

7x[cumulative dose of Dexamethasone during the first 2 cycles/ (min(date of first dose of Dexamethasone in the last cycle among the first 2 cycles+28, discontinuation date, death date) - date of first dose of Dexamethasone in cycle 1)]

Cycle 3 and beyond:

7x[cumulative dose of Dexamethasone staring from Cycle 3 / (min(date of first dose of Dexamethasone in the last cycle+28, discontinuation date, death date) - date of first dose of Dexamethasone in cycle 3)]

Age	Day	1	8	15	22
Cycles 1 and 2			•		
\leq 75 years old	Dexamethasone	28 mg PO +			
	(mg)	8 mg IV ^{a,b}			
> 75 years old	Dexamethasone	8 mg PO +			
	(mg)	8 mg IV ^{a,b}			
Cycles 3 and bey	ond				
≤ 75 years old	Dexamethasone	28 mg PO +	40 mg PO per	40 mg PO per	40 mg PO per
	(mg)	8 mg IV ^{a,b}	week ^c	week ^c	week ^c
> 75 years old	Dexamethasone	8 mg PO +	20 mg PO per	20 mg PO per	20 mg PO per
	(mg)	8 mg IV ^{a,b}	week ^c	week ^c	week ^c

Table 3: Dexamethasone Dosing, All Subjects Receiving Elotuzumab

^a On days of elotuzumab, infusion dexamethasone will be administered as a split dose of:

28 mg PO, for subjects \leq 75 years old or 8 mg PO for subjects > 75 years old (between 3 - 24 hours before the start of elotuzumab infusion)

AND

8 mg IV (on the day of elotuzumab infusion at least 45 minutes before the start of infusion)

^b If elotuzumab dosing is skipped or discontinued, dexamethasone will be administered orally as in days without elotuzumab.

^c Note the dexamethasone dose, as elotuzumab is not given on Days 8, 15 and 22 of cycle 3 and beyond.

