7.5 Efficacy

7.5.1 Progression-Free Survival

The primary analysis of this study is to estimate the two definitions of progression free survival (PFS) in all treated patients. The median PFS and 2-sided 95% confidence interval will be caculated via Kaplan-Meier (KM) estimation procedure. The PFS function will be estimated using the KM product limit method and will be displayed graphically. Estimates for 1-year, 2-year, and 3-year PFS rates will be presented along with their associated 95% CIs. These estimates will be come from the KM curve and their standard errors (SEs), for use in constructing CIs, will be computed using Greenwood's formula¹⁷ and on log-log transformation applied on the survivor function.

Analyses of PFS will be conducted based on all treated population, and also by subgroups based on lines of prior therapy (2L/3L groups), or by age group (<65 years, \geq 65 years), and (<75 years, \geq 75 years). Subgroup analysis by ECOG PS (0-1,2), by response to most recent line of therapy (relapsed and refractory, relapsed, refractory, intolerant) and by ISS stage (I,II,III) if albumin and beta 2 microglobulin data are available will be conducted as well. PFS is also evaluated based on 3 levels of response (VGPR or better, PR, SD or MR). PFS will be estimated using the Kaplan-Meier (KM) product limit method and presented using a KM curve.

Time from last tumor assessment to data cut-off in months will be summarized by treatment arm and overall for all treated subjects. Subjects who have a PFS event will be considered as current for this analysis.

A by-subject listing will be presented including PFS duration on all treated population, whether the subject was censored, and if censored, the reason.

All of the analyses will be repreated for primary and secondary definitions of PFS.

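### The exposure-adjusted AE rate credits every subject with 60 days after the last dose, with no cap at death, end of contact or data cut-off, so it is too low wherever that window is cut short

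*SAP*

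**What the plan says.** SAP 7.6.1 plans rates by system organ class and preferred term: "Exposure-adjusted incidence rate per 100 person-years will be used and will be calculated as". The denominator, as extracted with its typesetting braces, ends "subject date of first dose of study drug} + 60 + 1}{365.25", so a subject's person-time in years is (last dose − first dose + 60 + 1)/365.25. Repeat events count: "AEs can be counted multiple times within each SOC and preferred term in this summary table". The same section defines on-study AEs as those "with an onset date on or after the first dose until 60 days after the last dose". No term refers to death, last contact or data cut-off.

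Elsewhere the SAP does end a subject's time early. The dose-intensity denominators in 7.4.1.10 take a minimum that includes "discontinuation date, death date) - date of first dose of Pomalidomide". Section 7.5.1 works with a data cut-off ("Time from last tumor assessment to data cut-off in months"), and 7.5.2 uses last-known-alive dates.

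The SAP's 60 days apply to both cohorts. Protocol 6.2.1 collects nonserious AEs for 60 days in EPd but "until 100 days from the last dose of study drug for the EN cohort", and Protocol 8.4.3 gives the same 100 days for EN safety assessments.

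**The concern.** A person-time denominator should contain only time in which an event could have been recorded. A subject who dies soon after the last dose, is lost to follow-up, or is still being dosed at cut-off has not been observed for the 60 days credited. The error runs one way: extra time can only lower the rate.

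Such subjects are foreseeable. The EN primary analysis falls when enrolment is complete and "all enrolled patients treated with the combination have received at least 3 cycles of treatment", so late enrollees may still be on treatment. The EPd primary analysis is triggered by 48 events, which leaves up to about 12 of 60 subjects event-free and possibly still dosing. Protocol 8.5 also allows earlier administrative looks to support presentations or publications. At stake is a published safety rate that looks more favourable than the data.

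**Working it through.** The documents state no exposure-adjusted rate, person-years, exposure duration or early-death rate, so there is no planned figure to reproduce. The check compares the written formula with a capped one.

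**Per subject.** Let T = last dose − first dose in days, and d = days actually observed after the last dose (0 to 60).
- As written: T + 61 days.
- Capped: T + 1 + d days.
- Overstatement factor: (T + 61)/(T + 1 + d). The rate is multiplied by its inverse.

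| T | d=0 | d=14 | d=30 | d=60 |
|---|---|---|---|---|
| 28 | 89/29 = 3.07 | 89/43 = 2.07 | 89/59 = 1.51 | 1.00 |
| 70 | 131/71 = 1.85 | 131/85 = 1.54 | 131/101 = 1.30 | 1.00 |
| 365 | 426/366 = 1.16 | 426/380 = 1.12 | 426/396 = 1.08 | 1.00 |

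**An EN subject still on treatment at the earliest 3-cycle analysis.** Under Protocol 3.1, nivolumab on Cycle 3 Day 15 falls on study day 2×28 + 15 = 71, so T = 70. Cut-off after three cycles is day 84.
- As written: 70 + 61 = 131 days. Capped: 84 days.
- Factor 131/84 = 1.56; that subject's rate is 1 − 84/131 = 36% too low.

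**Cohort level.** This was simulated under assumptions that the documents do not supply:
- Exponential time on treatment.
- 5–30% of subjects who stop treatment die within the 60 days, uniformly over that period.
- For subjects still on treatment, the last dose falls 0–14 days before cut-off.
- No other loss to follow-up.

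For EPd, time on treatment uses the planned PFS hazard of 0.0462 per month (median 15 months) as a proxy, with 24 months' accrual and 24 more of follow-up. That timing fits the trigger: 60 × [1 − (e^(−0.0462×24) − e^(−0.0462×48))/(0.0462×24)] = 48.04 events. For EN, accrual is assumed to take 12 months and median time on treatment to be 2–6 months.

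| Setting | Person-time factor | Rate understated by (1 − 1/factor) |
|---|---|---|
| EPd at 48 events | 1.021–1.032 | 2.1–3.1% |
| EN, 3 cycles after last enrolment | 1.064–1.151 | 6.0–13.1% |
| EN, cut-off at month 36 | 1.008–1.064 | 0.8–6.0% |

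At the early EN analysis the factor rises with time on treatment: 1.064–1.119 at a median of 2 months and 1.127–1.151 at 6 months. More subjects are then still being dosed at cut-off. Cut-off, as well as early death, drives the cohort figure.

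**The case against.** The strongest reply is that the 60 days are deliberate and correct in principle. They match the 60-day on-study AE definition in the same section, so numerator and denominator agree and the bias is exactly zero for anyone observed throughout. That stands: the added 60 days are not the fault, only the missing cap.

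It is also fair that the output matters little to the trial's conclusions. It is an additional descriptive table shown with event counts. Worst-grade AE tables, SAE tables and deaths are unaffected; the rate is not among the topline safety outputs in SAP 9.1; and the EN stopping rules use percentages of treated patients. With the planned minimum of 24 months' follow-up, most windows will be complete by the end.

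SAP 8.4 refers AE handling to sponsor safety conventions that are not available here and might specify a cap. The explicit formula in 7.6.1 contains none, so the point stands as written, with that reservation.

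Three stronger readings are tempting and are not supported.
- **EN is affected most because its exposure is short.** Neither document gives EN exposure or early deaths, and EN non-responders may cross over and continue study drug. The ordering can also reverse: with EN cut off at month 36, a median of 4 months on treatment and 5% early deaths, the EN factor is 1.008, against 1.021 for EPd.
- **The 60-versus-100-day mismatch lowers the EN rate.** As the SAP stands, days 61–100 are outside both numerator and denominator. This is a separate inconsistency.
- **The large single-subject factors describe the table.** They apply only to subjects with truncated windows, and the table pools all subjects.

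**Conclusion.** The point holds as a person-time definition that should be capped. Followed exactly, the SAP 7.6.1 formula understates the rate for every subject whose 60-day window is cut short, by a relative amount that is larger the shorter the exposure, and it has no effect on other subjects.

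The direction follows from the formula alone. The cohort sizes (about 2–3% of person-time for EPd at 48 events, 6–15% for EN at the 3-cycle analysis, 1–6% for EN with long follow-up) rest on assumed accrual, time on treatment and early-death rates and should be read as ranges. They support no fixed ranking of the cohorts. Importance is low to moderate: a planned safety output with an avoidable bias in the favourable direction, on which no hypothesis test or stopping decision depends.

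**What to change.** In SAP 7.6.1, define person-time as the sum over subjects of

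min(last dose + 60 days, death date, last contact or withdrawal date, data cut-off) − first dose + 1, divided by 365.25.

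This keeps the 60-day numerator window. It is one formula and a small programming change, using dates the SAP already relies on; reported rates rise slightly or stay the same.

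Separately, reconcile the SAP's 60 days for EN with the 100 days in Protocol 6.2.1 and 8.4.3. Any new window must be set in the on-study AE definition and in the denominator together. Changing the denominator alone would add bias: a fully observed EN subject with T = 70 would go from 131 to 70 + 100 + 1 = 171 days, and the rate would fall by 1 − 131/171 = 23%. State the rule for EN subjects who cross over to EPd as well, since Protocol 6.2.1 requires a 100-day visit after the last nivolumab dose for those who stop within two EPd cycles.
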